## 4.3. Study Termination

The investigator retains the right to terminate study participation at any time, according to the terms specified in the study contract. The investigator/head of study site (Japan) is to notify the IRB/IEC in writing of the study's completion or early termination, send a copy of the notification to the sponsor or sponsor's designee, and retain 1 copy for the site study regulatory file.

The sponsor may terminate the study electively, if required by regulatory decision. If the study is terminated prematurely, the sponsor will notify the investigators/head of study site (Japan), the IRBs and IECs, and regulatory bodies of the decision and reason for termination of the study. For Japan, the head of study sites will notify the investigators and the IRBs of the decision and reason for termination of the study.

## 5. STUDY POPULATION

Deviations from eligibility criteria are not allowed because they can potentially jeopardize the scientific integrity of the study, regulatory acceptability, and/or participant safety. Therefore, adherence to the criteria as specified in the Protocol is essential. Prospective approval of Protocol deviations to recruitment and enrollment criteria, also known as Protocol waivers or exemptions, are not permitted.

### 5.1. Inclusion Criteria

Participants are eligible to be included in the study only if all of the following criteria apply:

1. Age 18 years or older, inclusive at the time of signing the informed consent; a legally minor participant from Japan needs written parental or legal guardian's consent.
2. Histologically or cytologically confirmed solid tumor malignancy that is advanced or metastatic (Stage IIIB or IV per the AJCC Cancer Staging Manual, 8th ed; [AJCC 2018](#)) or is surgically unresectable.
3. Radiographically measurable disease (per RECIST v1.1 or RANO for primary brain tumors). Tumor lesions located in a previously irradiated area, or in an area subjected to other loco-regional therapy, are considered measurable if progression has been clearly demonstrated in the lesion.
4. Documentation of an FGFR1-3 gene mutation or fusion/rearrangement (see Section [8.5.1](#) and [Appendix C](#)). Participants will be assigned to 1 of 3 cohorts:
  - Cohort A: FGFR1-3 in-frame fusions; any FGFR2 rearrangement; FGFR1/3 rearrangement with known partner\* (n = 60)
  - Cohort B: Known or likely activating mutations (excluding kinase domain) in FGFR1-3 included in [Appendix C](#) (n = 90)
  - Cohort C: FGFR1-3 known activating mutations in kinase domain; FGFR1-3 putatively activating mutations; other FGFR1/3 rearrangements\* (not eligible for Cohort A; n = 20)

\*Only FGFR fusions or rearrangements with an intact kinase domain are eligible.

5. Must have objective progression after at least 1 prior therapy, and must have no therapy available that is likely to provide clinical benefit. Participants who are intolerant to or decline the approved therapy are eligible only if they have no therapy available that is likely to provide clinical benefit.
6. ECOG performance status 0 to 2.

7. Baseline archival tumor specimen (if less than 24 months from date of screening) or willingness to undergo a pretreatment tumor biopsy to obtain the specimen. Must be a tumor block or approximately 15 unstained slides from biopsy or resection of primary tumor or metastasis.
8. Willingness to avoid pregnancy or fathering children based on the criteria below.
  - a. Men must agree to take appropriate precautions to avoid fathering children (with at least 99% certainty) from screening through 90 days after the last dose of study drug(s)/treatment and must refrain from donating sperm during this period. Permitted methods that are at least 99% effective in preventing pregnancy (see [Appendix A](#)) should be communicated to the participants and their understanding confirmed.
  - b. Women of childbearing potential must have a negative serum pregnancy test at screening and before the first dose on Day 1 and must agree to take appropriate precautions to avoid pregnancy (with at least 99% certainty) from screening through safety follow-up. Permitted methods that are at least 99% effective in preventing pregnancy (see [Appendix A](#)) should be communicated to the participants and their understanding confirmed.
  - c. Women of nonchildbearing potential (ie, surgically sterile with a hysterectomy and/or bilateral oophorectomy OR  $\geq 12$  months of amenorrhea) are eligible.
9. For Japanese participants, willingness to avoid pregnancy or fathering children based on the criteria below.
  - a. Female participants should agree to use medically acceptable contraceptive measures (see [Appendix A](#)), should not be breastfeeding, and must have a negative pregnancy test before the start of study treatment administration if of childbearing potential. All female participants of childbearing potential must understand and accept that pregnancy must be avoided during participation in the study from screening through 30 days after the last dose of pemigatinib (based on menstrual cycle).

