**Table 4: Schedule of Laboratory Assessments**

Visit Day (Range)	Screening	Treatment			EOT	Follow-Up		Survival	Notes
	Days -35 to -1	Cycle 1		Cycles 2+		Safety	Disease		
		Day 1	Day 8 (± 3 d)	Day 15 (± 3 d)		Day 1 (± 3 d)	(EOT + 30-35 d)		
							Every 9 wk ± 7 d		
Clinical laboratory assessments									
Blood chemistries	X	X*	X	X	X**	X	X		*If screening performed within 3 days of C1D1, additional sample not required. **HP in Cycle 1 requires Day 8 testing of serum phosphate in Cycle 2+.
Hematology	X	X*			X	X			*If screening performed within 3 days of C1D1, additional sample not required.
Coagulation	X	X			X	X			*If screening performed within 3 days of C1D1, additional sample not required.
Endocrine (PTH only)	X				X*	X			*Every 3 cycles on Day 1 starting with Cycle 3.
HBV/HCV testing	X								
Urinalysis	X					X			
Pregnancy testing	X*	X			X	X*			*Serum.
translational laboratory assessments									

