## OR

Female participants must have evidence of nonchildbearing potential by fulfilling 1 of the following criteria at screening:

- Postmenopausal, defined as aged  $> 50$  years and amenorrheic for at least 12 months after cessation of all exogenous hormonal treatments.

Note: Female participants who have been amenorrheic for at least 12 months resulting from chemotherapy/radiotherapy are considered of childbearing potential and should agree to use adequate contraceptive measures.
- Documentation of irreversible surgical sterilization by hysterectomy, bilateral oophorectomy, or bilateral salpingectomy but not tubal ligation.

- b. Male participants should avoid unprotected sex with females of childbearing potential during the study and for a washout period of 90 days after the last dose of pemigatinib. Male participants should refrain from donating sperm from the start of the study treatment administration until 90 days after discontinuing study treatment.

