### **8.3.6.1. Pregnancy Testing**

[figure not shown]
A serum pregnancy test will be required for all women of childbearing potential during screening and at the EOT visit; participants going into hospice are not required to provide EOT pregnancy test. Urine pregnancy tests will be performed locally on Day 1 of each cycle, as outlined in [Table 4](#), as medically indicated (eg, in case of loss of menstrual cycle, when pregnancy is suspected), or per country-specific requirement (note that country-required urine pregnancy testing will be outlined and communicated to investigational sites under separate cover). If a urine pregnancy test is positive, the results should be confirmed with a serum pregnancy test.

If the serum pregnancy test is negative after a urine test was positive, the investigator will assess the potential benefit/risk to the participant and determine whether it is in the participant's best interest to resume study drug and continue participation in the study.

If a pregnancy is confirmed by a serum pregnancy test, see Section [9.5](#) for reporting requirements.

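### Outside Japan, criterion 8c counts 12 months of amenorrhea from chemotherapy or radiotherapy as nonchildbearing potential, which removes the contraception duty and the serum pregnancy tests

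*Protocol*

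**What the plan says.** Protocol 5.1, criterion 8c, sets out who is of nonchildbearing potential: "Women of nonchildbearing potential (ie, surgically sterile with a hysterectomy and/or bilateral oophorectomy OR" at least 12 "months of amenorrhea) are eligible". The parenthesis opens with ie, so it is a definition and not a list of examples. Appendix A lists contraceptive methods but does not define the term, and no other section defines it for participants outside Japan.

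The duties attach to the opposite class. Criterion 8b begins "Women of childbearing potential must have a negative serum pregnancy test at screening and before the first dose on Day 1" and goes on to require contraception from screening through safety follow-up. Section 8.3.6.1 adds: "A serum pregnancy test will be required for all women of childbearing potential during screening and at the EOT visit".

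Criterion 9 applies to Japanese participants only. Its postmenopausal route (9a) requires age over 50 and counts a woman only if she has been "amenorrheic for at least 12 months after cessation of all exogenous hormonal treatments". The Note under it says: "Female participants who have been amenorrheic for at least 12 months resulting from chemotherapy/radiotherapy are considered of childbearing potential". Appendix F, Amendment 3 item 11, gives recommended standard practice in Japan as the reason for adding criterion 9.

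**The concern.** Everyone in this trial has been treated before. Criterion 5 requires progression after at least one earlier therapy, entry is open from age 18, and SAP 6.1.4 plans summaries of earlier systemic regimens and radiation. Amenorrhea caused by treatment is therefore foreseeable among the younger women. The Note in 9a shows that the sponsor does not regard 12 months of it as evidence that a woman cannot conceive.

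At stake is pregnancy while on pemigatinib. Section 7.1.1 lists pregnancy as a reason to stop study treatment. Section 9.5 requires immediate interruption and classes abnormal pregnancy outcomes in a participant as serious adverse events. Criterion 8 exists to prevent this, yet followed exactly it drops the preventive step for these women. Section 5 allows no deviation from the eligibility criteria, so this outcome follows from the rule as written.

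**Working it through.** No figure in the plan bears on this point, so the check is a reading of the text. Take a 35-year-old woman, not surgically sterile, with 12 months of amenorrhea caused by earlier chemotherapy.

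**Classification**

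| | Outside Japan | Japan |
|---|---|---|
| Governing text | 8c | 8 and 9a together |
| Age condition for amenorrhea | none | over 50 |
| Cause of amenorrhea | not considered | chemotherapy or radiotherapy means childbearing potential |
| Exogenous hormones | not considered | 12 months must follow cessation |
| Result for this woman | nonchildbearing potential | childbearing potential |

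In Japan both criteria bind, because "Participants are eligible to be included in the study only if all of the following criteria apply". The stricter 9a therefore prevails there. Elsewhere nothing overrides 8c.

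**What she no longer owes outside Japan**

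1. Contraception under 8b, from screening through safety follow-up. That is her whole time in the study, which Table 2 estimates at about 6 months.
2. Serum tests. Criterion 8b names screening and before the first dose; 8.3.6.1 names screening and end of treatment. The distinct time points are screening, Day 1 and end of treatment, so 3. Table 4 marks serum only at screening and end of treatment, and 8.3.6.1 describes the Day 1 test as urine. On that reading the count is 3 − 1 = 2.

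**What appears to remain**

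1. The row "Pregnancy testing" in Table 4 names no population. The sentence in 8.3.6.1 on local urine tests on Day 1 of each cycle does not repeat the childbearing-potential limit. On the wording, she is still tested on those days. Section 8.3.6 requires Day 1 laboratory samples to be taken before dosing.
2. A positive urine test should be confirmed by serum (8.3.6.1).
3. Exclusion 23 bars pregnant women, but adds no test.
4. Section 8.3.6.1 also allows testing when medically indicated, with loss of the menstrual cycle as an example. That prompt is of doubtful use in a woman who already has no cycle.

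Each remaining item detects or bars a pregnancy. None prevents one.

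**The hormone route** is narrower. Exclusions 2 and 3 bar anticancer medication in the 28 days before the first dose and concurrent anticancer hormonal therapy. That leaves mainly hormones taken for other reasons. If the hormone is an ovulation-inhibiting contraceptive, Appendix A already counts it as highly effective.

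**The case against.** The strongest reply is that the only benchmark is a regional rule. Criterion 9 was added for Japanese practice and says nothing about other regions. Appendix A rests on an external contraception recommendation that is not among the documents. Country-specific urine testing is communicated separately and the consent pages are not public, so sites and participants may be told more than can be seen here. Exclusion 24 also lets an investigator keep out a woman at significant risk.

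Part of this stands. A reader might infer that 8c and 9a contradict each other. They do not, because each has its own scope. But drug and regimen are the same in every region, and the documents give no reason why reversible amenorrhea should be judged differently outside Japan. Investigator discretion does not supply a contraception duty that the criterion removes.

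A reader might also infer that these women go untested. The wording on Day 1 urine tests does not support that. Nor should the loss be put firmly at three serum tests, since that needs the less favourable reading of Day 1. Days without a contraception duty do not measure harm either. Adding screening and follow-up to the 6 months is doubtful as well, because Table 2 gives that estimate for participation after listing all three periods.

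**Conclusion.** The point holds, at modest size. Outside Japan, a woman of reproductive age with at least 12 months of amenorrhea from earlier chemotherapy or radiotherapy is classed as of nonchildbearing potential. The same applies, less often, to amenorrhea from non-anticancer hormones. She owes no contraception for the length of her participation and misses two serum pregnancy tests, or three if Day 1 is read as serum.

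This rests on two readings: that 8c is applied as written, and that Day 1 urine tests cover all women, as the wording of 8.3.6.1 and Table 4 suggests. If sites limit those urine tests to women of childbearing potential, the gap is wider.

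The documents give no count of women, of their ages or of amenorrhea, so the number affected cannot be determined and may be small. The prior-therapy summaries in SAP 6.1.4 show that the exposures are expected, not how often amenorrhea follows. Response rate, cohort assignment, alpha and power are unaffected. This is a cheap improvement for patient safety.

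**What to change.** Keep the surgical limb of 8c and replace the amenorrhea limb with:

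> At least 12 months of amenorrhea not resulting from chemotherapy, radiotherapy or current exogenous hormonal treatment. Women aged 50 years or younger who were not postmenopausal before such treatment, and whose amenorrhea results from it, are considered of childbearing potential. Women older than 50 years with at least 12 months of amenorrhea off exogenous hormones remain of nonchildbearing potential.

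The bound of 50 comes from 9a. Without it, a clearly postmenopausal older woman whose periods stopped with chemotherapy years ago would be reclassed for no benefit. Leave 9a as it is; it stays stricter for Japan.

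The cost is one amended criterion, with contraception and pregnancy tests already in the protocol extended to a few more women. Some of them will in fact be permanently infertile and will not need the measures. A reclassed woman who agrees to contraception and tests negative remains eligible under criterion 8; one who declines would not.

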## OR

Female participants must have evidence of nonchildbearing potential by fulfilling 1 of the following criteria at screening:

- Postmenopausal, defined as aged  $> 50$  years and amenorrheic for at least 12 months after cessation of all exogenous hormonal treatments.

Note: Female participants who have been amenorrheic for at least 12 months resulting from chemotherapy/radiotherapy are considered of childbearing potential and should agree to use adequate contraceptive measures.
- Documentation of irreversible surgical sterilization by hysterectomy, bilateral oophorectomy, or bilateral salpingectomy but not tubal ligation.

- b. Male participants should avoid unprotected sex with females of childbearing potential during the study and for a washout period of 90 days after the last dose of pemigatinib. Male participants should refrain from donating sperm from the start of the study treatment administration until 90 days after discontinuing study treatment.

## 5.2. Exclusion Criteria

Participants are excluded from the study if any of the following criteria apply:

1. Prior receipt of a selective FGFR inhibitor.
2. Receipt of anticancer medications or investigational drugs for any indication or reason within 28 days before first dose of pemigatinib. Participants must have recovered ( $\leq$  Grade 1, as per CTCAE v5.0, or at pretreatment baseline) from AEs from previously administered therapies (excluding alopecia).
3. Concurrent anticancer therapy (eg, chemotherapy, radiation therapy, surgery, immunotherapy, biologic therapy, hormonal therapy, investigational therapy, or tumor embolization).
4. Candidate for potentially curative surgery.
5. Current evidence of clinically significant corneal (including, but not limited to, bullous/band keratopathy, corneal abrasion, inflammation/ulceration, keratoconjunctivitis) or retinal disorder (including, but not limited to, macular/retinal degeneration, diabetic retinopathy, retinal detachment) as confirmed by ophthalmologic examination.
6. Radiation therapy administered within 2 weeks of enrollment/first dose of study treatment. Participants must have recovered from all radiation-related toxicities, not require corticosteroids, and not have had radiation pneumonitis. Evidence of fibrosis within a radiation field from prior radiotherapy is permitted with medical monitor approval. A 1-week washout is permitted for palliative radiation to non-CNS disease.
7. Untreated brain or CNS metastases or brain or CNS metastases that have progressed (eg, evidence of new or enlarging brain metastasis or new neurological symptoms attributable to brain or CNS metastases). Participants who have previously treated and clinically stable brain or CNS metastases are eligible if there is no evidence of progression for at least 4 weeks after CNS-directed treatment, as ascertained by clinical examination and brain imaging (MRI or CT scan) during the screening period, and if they are on a stable or decreasing dose of corticosteroids for at least 1 week.

*Note:* Participants with progressing primary brain tumors are allowed if they have no new neurological symptoms and are on a stable or decreasing dose of corticosteroids for at least 1 week.

8. Known additional malignancy that is progressing or requires active treatment. Exceptions include basal cell carcinoma of the skin, squamous cell carcinoma of the skin, or *in situ* cervical cancer that has undergone potentially curative therapy.
9. Participants with laboratory values at screening defined in [Table 10](#).

**Table 10: Exclusionary Laboratory Values**

Laboratory Parameter		Exclusion Criterion
Hematology		
a	Platelets	$\leq 75 \times 10^9/L$ (transfusion allowed with a 2-week washout period)
b	Hemoglobin	$\leq 9.0 \text{ g/dL}$ (transfusion allowed with a 2-week washout period)
c	ANC	$\leq 1.5 \times 10^9/L$
Hepatic		
e	ALT	$\geq 3 \times \text{ULN}$ ( $> 5 \times \text{ULN}$ for liver metastasis)
f	AST	$\geq 3 \times \text{ULN}$ ( $> 5 \times \text{ULN}$ for liver metastasis)
g	Total bilirubin	$\geq 1.5 \times \text{ULN}$ ( $\geq 2.5 \times \text{ULN}$ if Gilbert's syndrome or liver metastasis)
h	Alkaline phosphatase	$\geq 3 \times \text{ULN}$
Renal		
i	Serum creatinine clearance	$\leq 30 \text{ mL/minute}$ based on Cockcroft-Gault formula.
Chemistry		
j	Serum phosphate	$> \text{ULN}$
k	Serum calcium	Outside of normal range or serum albumin-corrected calcium outside of the normal range when serum albumin is outside of the normal range.

10. History of calcium and phosphate hemostasis disorder or systemic mineral imbalance with ectopic calcification of soft tissues (exception: commonly observed calcifications in soft tissues such as the skin, kidney tendon, or vessels due to injury, disease, or aging in the absence of systemic mineral imbalance).
11. Significant gastrointestinal disorder(s) that could interfere with absorption, metabolism, or excretion of pemigatinib.
12. Inability to swallow and retain oral medication.
13. Clinically significant or uncontrolled cardiac disease, including unstable angina, acute myocardial infarction within 6 months from Day 1 of study drug/treatment administration, New York Heart Association Class III or IV congestive heart failure, and uncontrolled arrhythmia (participants with pacemaker or with atrial fibrillation and well-controlled heart rate are allowed).
14. History or presence of an abnormal ECG that, in the investigator's opinion, is clinically meaningful. A screening QTcF interval  $> 480 \text{ ms}$  is excluded. For participants with an intraventricular conduction delay (QRS interval  $> 120 \text{ ms}$ ), the JTc interval may be used in place of the QTc with medical monitor approval. The JTc must be  $\leq 340 \text{ ms}$  if JTc is used in place of the QTc.

15. Active chronic or current infectious disease requiring systemic antibiotic, antifungal, or antiviral treatment within 2 weeks before enrollment (participants with asymptomatic chronic infections on prophylactic treatment are allowed).
16. Evidence of active HBV or HCV infection (defined as participants with elevated transaminases or cirrhosis. Participants with chronic HBV/HCV infection with no cirrhosis and no elevated transaminases are allowed).
17. Known HIV infection.
18. Current use of prohibited medication as described in Section [6.6.2](#).
19. Use of any potent CYP3A4 inhibitors or inducers or moderate CYP3A4 inducers within 14 days or five half-lives (whichever is longer) before the first dose of study drug/treatment. Note that moderate CYP3A4 inhibitors are not prohibited.
20. Known hypersensitivity or severe reaction to pemigatinib or excipients of pemigatinib (refer to the [IB](#)).
21. Inability or unlikelihood of the participant to comply with the dose schedule and study evaluations, in the opinion of the investigator.
22. Inadequate recovery from toxicity and/or complications from a major surgery before starting therapy.
23. Women who are pregnant or breastfeeding.
24. Any condition that would, in the investigator's judgment, interfere with full participation in the study, including administration of study drug/treatment and attending required study visits; pose a significant risk to the participant; or interfere with interpretation of study data.
25. Inability of the participant (or parent, guardian, or legally authorized representative) to comprehend the ICF or unwillingness to sign the ICF.
26. History of hypovitaminosis D requiring supraphysiologic doses (eg, 50,000 UI/weekly) to replenish the deficiency. Vitamin D supplements are allowed.

